#### Analytical methods

Continuous variables will be described by their mean, standard deviation, median, quartiles 1 and 3, extreme values (minimum and maximum) and the number of missing data.

Categorical variables will be described by the total and percentage of each response method and the number of missing data.

Continuous variables will be compared using Student's t-test (2 groups) or variance analysis (>2 groups). If the conditions for applying these tests are not met (normality, homoscedasticity), the Mann-Whitney, Wilcoxon (2 groups) or Kruskal-Wallis (>2 groups) non-parametric tests will be used.

Categorical variables will be compared between subgroups using the Chi-2 test if the theoretical total of each class studied is greater than 5. Otherwise Fisher's exact test will be used.

The ordinal variables will be compared between subgroups using a Cochran-Mantel-Haenszel test.

Hypothesis formulation will be bilateral. The tests will be performed for a first species alpha risk of 5%.

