
## 5.4 Sample Size Calculation

Data for this pregnancy Registry will be regularly collected until the sample size required to detect a 2-fold or greater increase relative to the expected background rate of all birth defects and spontaneous abortions is reached. This will provide an adequate sample to ensure understanding of maternal drug safety. The Registry will be closed to new entries once this number of women with validated follow-up information has been reached and in agreement with the EMA; the data will be transferred to another independent Registry, if in acceptance with the other Registry, and according to ethical standards and national legislation at that point in time. These data will then be compared to background rates to see if there has been a significant increase in birth defects or pregnancy loss amongst these patients. A sensitivity analysis will be performed on the data to check other contributing factors.

The following sample size is derived to detect a clinically significant difference (i.e. a >2x increase in the outcome of concern) relative to expected background rates. In Europe, the assumed background risk of all reported birth defects is 23.719 per 1,000 births (EUROCAT, 2009) and the background rate of spontaneous abortion is 85.6 per 1,000 (Tata *et al*, 2005). Thus, assuming 80% power, 0.05 significance level (one-sided) and a loss to follow-up rate of 5%, we would require 376 pregnant women exposed to EurartesimTM in order to be able to detect a 2-fold or greater increase in birth defects and a 1.5-fold or greater incidence in spontaneous abortions with a one-group test. Calculations are based on a normal approximation to a Binomial distribution (equivalent to a chi-square test). Employing a 5% loss to follow-up rate is deemed appropriate as

utilising the services of ProClinica (refer to Section 7.3) to actively follow-up patients via direct patient contact should reduce the degree of loss to follow-up in this Registry.

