## 5.7 Statistical analysis

Statistical analyses will be carried out using SAS software version 9.2.

R-M EU will prepare a statistical analysis plan to be reviewed by Sigma-Tau and the CAB.

At regular intervals tables and listings will be produced to enable reporting of key interim outcomes to regulatory authorities, participating HCPs and the scientific/medical community at large.

Reporting of data (other than individual reports concerning individual patients or participating HCPs to those individual participants), will be in aggregate form to ensure individual patient and HCP confidentiality.

All analyses, primary and secondary, will be conducted in two manners:

- 1. On all women.
- 2. Stratifying the women depending on whether they were directly exposed to Eurartesim™ or whether the biological father was exposed to Eurartesim™.

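### Switching to Mann-Whitney or Kruskal-Wallis when variances differ only partly repairs the comparison of means, so the stated two-sided 5% does not hold in unequal subgroups (minor point)

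*Protocol*

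**What the plan says.** Protocol Section 5.7, *Analytical methods*, sets the default: "Continuous variables will be compared using Student's t-test (2 groups) or variance analysis (>2 groups"). It then gives the exception: "If the conditions for applying these tests are not met (normality, homoscedasticity), the Mann-Whitney, Wilcoxon (2 groups) or Kruskal-Wallis" tests replace them. The Summary repeats the rule in its statistical analysis entry.

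The same paragraph fixes sidedness and level for these tests: "Hypothesis formulation will be bilateral", and "The tests will be performed for a first species alpha risk of 5" per cent.

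The rule names no variables and no groups. Nearby text divides the women in several ways. Section 5.7 runs every analysis on all women and again by route of exposure ("Stratifying the women depending on whether they were directly exposed to" the drug or had an exposed partner). *Pregnancy-related information* tabulates outcomes by earliest trimester of exposure, demographics and medical background, and analyses first and recurring malaria apart. Gestational age at delivery is a listed secondary outcome (Section 7.4.1), and infant birth weight is collected at the end of pregnancy (Section 5.5).

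**The concern.** The rule treats a rank test as the cure for both non-normality and unequal variance. It can help with the first but is not designed for the second. Mann-Whitney guarantees 5% when the two distributions are identical, and once variances differ that hypothesis is already false. As a test of equal means, or of an even chance that a woman in one group exceeds a woman in the other, it uses a standard error that is wrong whenever sizes and variances both differ.

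The error can go either way. If the smaller subgroup is the more variable, the test rejects too often and a safety registry sees differences that are not there. If the larger subgroup is the more variable, the test rejects too rarely and real differences are missed. Which case applies is unknown in advance. The switch also lets the data decide whether the comparison concerns means or ranks.

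**Working it through.** **Inputs.** From Section 5.4: 376 women with 5% loss, so 376 × 0.95 = 357 evaluable. From Section 5.7: two-sided 5%, critical value 1.96. Assumed, because the protocol gives none: splits of 327/30 and 250/107 (each totals 357), SD ratios of 1.5 and 2 in both directions, normal data with equal means, and a Levene test at 5% as the variance check.

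**Step 1: the stated 5%.** Let the groups have sizes m and n and SDs s and t. Mann-Whitney assumes that the estimated probability of X exceeding Y has variance V0 = (1/m + 1/n)/12. For normal data with equal means the true variance is approximately V = a/m + b/n, with a = arcsin[s²/(s²+t²)]/(2π) and b = arcsin[t²/(s²+t²)]/(2π). With equal SDs, a = b = arcsin(0.5)/(2π) = 1/12, so V = V0 and the error is 5%. Simulation with equal SDs at 36 vs 321 agrees (5.1%).

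**Step 2: unequal SDs.** The error is 2[1 − Φ(1.96/√R)], where R = V/V0.

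- Smaller group (30) twice as variable: a = arcsin(0.8)/(2π) = 0.1476 and b = arcsin(0.2)/(2π) = 0.0320. V = 0.1476/30 + 0.0320/327 = 0.00502 and V0 = 0.00303. R = 1.65, 1.96/1.286 = 1.524, error 12.8%.
- Larger group (327) twice as variable: V = 0.0320/30 + 0.1476/327 = 0.00152. R = 0.50, 1.96/0.708 = 2.769, error 0.6%.

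For Student's test, R is (s²/m + t²/n) divided by the pooled variance times (1/m + 1/n). In the first case the pooled variance is (29×4 + 326×1)/355 = 1.245. Then R = 0.1364/(1.245 × 0.0364) = 3.01 and the error is 25.9%.

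**Step 3: the two-step rule.** Simulated with 4,000 replicates: Levene at 5%, then Mann-Whitney if it rejects, otherwise Student. The formula columns apply step 2 to each row.

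| Split | SD of smaller group relative to larger | Two-step rule, simulated | Mann-Whitney, formula | Student, formula |
|---|---|---|---|---|
| 327/30 | ×1.5 | 10.3% | 9.6% | 16.0% |
| 327/30 | ×2 | 13.0% | 12.8% | 25.9% |
| 327/30 | ÷1.5 | 1.7% | 1.7% | 0.6% |
| 327/30 | ÷2 | 0.5% | 0.6% | 0.1% |
| 250/107 | ×1.5 | 7.7% | 7.4% | 9.4% |
| 250/107 | ×2 | 9.5% | 9.2% | 12.5% |
| 250/107 | ÷1.5 | 3.7% | 3.4% | 2.2% |
| 250/107 | ÷2 | 3.0% | 2.8% | 1.2% |

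Near an even split the departure is small: Mann-Whitney error is about 6% at SD ratio 2.

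**Step 4: more than two groups.** Kruskal-Wallis with assumed sizes 36/107/214 gives 10.0% when the smallest group has the largest SD and 2.6% in reverse.

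**Step 5: the alternative.** On normal data, for splits 327/30, 300/57 and 250/107 at the same four SD ratios, Welch's test stays at 4.6% to 5.5% and Brunner-Munzel at 4.5% to 5.8%. With strongly left-skewed data (a reversed exponential, also assumed), Welch rises to 6.6% to 7.4% at 327/30 and 7.6% to 8.9% at 339/18. Mann-Whitney read as a test of means reaches 30% with such data at 327/30 and SD ratio 1.5.

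**The case against.** Four objections deserve weight.

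First, a reader might infer that direct versus paternal exposure, trimester, and first versus recurring malaria are planned tests that this rule will serve. The documents do not say so. Section 5.7 stratifies or analyses these groups separately, and what it breaks down by trimester is the frequency and type of outcome, which is categorical. *Analytical methods* says only that continuous variables are compared. This stands: the rule is fixed, but its targets are not.

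Second, very unequal subgroups are an inference. The nearest support is Appendix 1, which expects few Caucasian women. Eligibility through the father is also confined to the 30 days before conception (Section 5.2), which suggests a small paternal group. No sizes or SDs appear. This stands too, although 250 to 107 is a moderate split and already shows the effect.

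Third, the protocol names no Levene test and no threshold, and the simulation leaves out the normality trigger, so it is one reading of the rule. How assumptions are checked may belong in the statistical analysis plan. The replacement test, however, is fixed in the protocol, and step 2 gives Mann-Whitney's error without any pre-test.

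Fourth, Mann-Whitney is valid for identical distributions, and the protocol does not state that its null is equal means. That is correct. But the test it replaces concerns means, and the trigger is evidence that the distributions differ.

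**Conclusion.** The point holds as a minor one. When variances and group sizes both differ, the replacement test does not deliver the stated two-sided 5% as a test of means. Under the assumptions above, error is about 10% to 13% at 327/30 and 8% to 10% at 250/107 when the smaller group is 1.5 to 2 times more variable. In reverse it is about 2% to 0.5% and 4% to 3%.

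Two stronger readings are not supported. One is that the switch makes matters worse. On normal data it lands nearer to 5% than Student's test in every row of the table, so it is an incomplete remedy. The other is that the registry's main conclusions are at risk. The primary analysis estimates incidences of birth defects and spontaneous abortion with 95% confidence intervals, and the 376 in Section 5.4 comes from a one-group test of proportions. Neither uses this rule. What is affected is secondary, exploratory comparison of continuous variables between subgroups, such as gestational age at delivery or birth weight.

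**What to change.** In Section 5.7, *Analytical methods*, and in the matching Summary text, name Welch's t-test (two groups) and Welch's analysis of variance (more than two groups) as the method for continuous variables, with no preliminary variance test. For variables expected to be markedly skewed, name in advance a rank analysis that remains valid under unequal variances, such as Brunner-Munzel. State that it addresses the probability that one group exceeds the other, not a difference in means.

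The cost is a sentence in two places and a negligible loss of power when variances are equal. Welch's test is not exact either: with strong skew and a small subgroup of about 30 it may run at 6% to 7%, and somewhat higher with fewer women. That is a reason to read such comparisons cautiously, not to keep the present rule.

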## 6. Bias and limits of the study

Generally, three types of bias are distinguished in epidemiology and should be considered: selection, information and confounding bias. Potential biases and limitations of the Eurartesim™ pregnancy Registry include:

## 6.1 Selection bias

Selection bias is a distortion of evidence or data that arises from the way that the data are collected.

The selection bias that could possibly occur in this study are related to the selection of the participating HCPs and the selection of patients.

#### HCP's representativeness:

The participating HCPs will consist of a population of volunteers; this constitutes a classical non-response selection bias for this type of study.

To describe this potential bias, we propose to compile a HCP recruitment registry in order to collect information (e.g. age, gender, speciality, geographic region, mode of practice, institution type) for all the contacted HCPs and for all the HCPs that initiate a contact themselves, participating or non-participating to the study. The reasons for nonparticipation will also be collected in the registry. These data will allow comparison of the characteristics of participating and non-participating HCPs.

#### **Patient's representativeness:**

In order to limit the patients' selection bias, the HCPs will have to consecutively include all the patients meeting the selection criteria. For all non-included patients meeting the selection criteria, the HCP will collect few data (e.g. age, gender, reason for noninclusion), in order to allow comparison of the characteristics of included and nonincluded patients.

It is anticipated that the primary limitation encountered when compiling this pregnancy registry will be patient recruitment as there may be very few women across Europe who have had malaria and also taken Eurartesim™ to treat such whilst pregnant. Thus, recruitment will be kept simple to optimize patient recruitment, i.e. both first and recurrent malaria infections will be included in this pregnancy Registry. This approach will be evaluated throughout the feasibility study and via discussions with Key Opinion Leaders in this field. Patient recruitment and data collection will be conducted as described above in this protocol.

Selection bias could also occur in this study regarding the inclusion of women who already know the health status of the foetus at the time of enrolment into the pregnancy registry, as patients with a known undesirable outcome may be more likely to enroll than Page **34** of **56** 

those with a known healthy outcome. However, due to the possible limitations regarding patient recruitment (as discussed above), women who already know the health status of the foetus at the time of enrolment into the pregnancy registry will still be eligible for inclusion.

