## 5.3 Health Care Providers (HCP) Selection Criteria

HCPs known to treat and follow-up malaria patients will be invited to collaborate in this Registry. Women who are not part of one of the selected sites will be able to contact their HCP who will contact Sigma-Tau on their behalf in order to be included in the Registry. In addition, all patients with pregnancies reported to the company as spontaneous events by HCPs will also be asked to participate in the pregnancy Registry. All spontaneous events (e.g. pregnancy exposure, birth defects) will be reported, regardless of the country they are coming from.

An invitation letter will be sent out with a summary of the study and a reply form to identify HCPs in each country. Non-respondent HCPs will be contacted by telephone by Epidemiologic Research Associates (ERAs) trained for this study, to determine the status regarding their participating.

The reply form and qualification telephone call will enable the collection of information about the sites (e.g. speciality, type of institution/practice, number of patients seen, reasons for refusal) and the assessment of their ability and willingness to participate.

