#### 5.3.1 Educational Outreach Program

An educational 'outreach program' will be implemented to increase awareness of the Registry among both patients and Health Care Providers (HCPs), and increase both patient and HCP participation.

The awareness campaign will include the following elements in each country initiated into the study:

- Patient Information Sheet included with product packaging (including contact data for each country).
- Targeted educational material.
- Registry website and web awareness activities, including internet based recruitment.
- Advertising and scientific presentations at specifically targeted meetings such as the tropical medicine society meetings, etc.
- Partnering with interested organisations.

Educational material, targeting those in traveller's medicine and infectious disease, will inform HCPs of the Registry and provide information on how they can refer patients for inclusion and participation.

A Registry website will provide information regarding the Registry, targeted at both patients and HCPs, and will describe the process for participation for both patients and HCPs, including relevant contact details; this website will be designed with a section for patients and a section for HCPs.

Internet based recruitment, using keyword searches, will also be employed. When an internet user uses a search engine, relevant keywords (e.g. malaria, EurartesimTM) will be rerouted to the Registry website, thus, raising awareness of the Registry and providing a means of both patient and HCP participation.

Additional web awareness activities will include placing advertisements and links on relevant sites (i.e. Medicines for Malaria Venture [MMV]).

There will also be advertising at annual professional society meetings (such as the European Society of Clinical Microbiology and Infectious Diseases) to increase HCP awareness and encourage referral of appropriate patients.

Page 22 of 56

In addition, the Sponsor will contact these organisations in an effort to increase awareness of the Registry to the public and HCPs:

- European Network of Teratogen Information Services (ENTIS)
- European Surveillance Network of Congenital Anomalies (EUROCAT)
- European Collaboration of Craniofacial Anomalies (EUROCRAN)
- International Clearinghouse for Birth Defects Monitoring Systems

A review of literature will be performed routinely to ensure that HCPs publishing any relevant maternal exposure are contacted for inclusion in the Registry.

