#### At enrolment visit:

- Date of the visit.
- Socio-demographic characteristics of the mother (ethnicity [based on the standard definitions of ethnicity used in the EU country where the woman is enrolled in the Registry], country of birth, primary language and socio-economic status [based on current or most recent occupation and years of formal education]).
- Socio-demographic characteristics of the biological father (age and current or most recent occupation).
- Mother's lifestyle data (height [cm] and weight [kg], radiation exposure, smoking status [never/past/current], alcohol consumption [weekly units], recreational drug use.
- Mother's malaria history (date of malaria diagnosis, date of most recent Eurartesim™ administration and dose, previous Eurartesim™ administrations, other treatment taken for malaria).
- Pregnancy data (date the pregnancy was registered).
- Estimated date of delivery/date of last menstrual period.
- Previous or concurrent maternal complications.
- Health status of the fetus, if it is already known at time of enrolment, i.e. via ultrasound.
- Pregnancy outcome, if already known at time of enrolment.

- Obstetrical history (number of previous pregnancies and outcome).
- Significant medical history of the mother and the biological father.
- Concomitant medication use in the mother and the biological father in the one (1) month (30 days) prior to conception.

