#### Primary analysis

In accordance with the primary objectives of the study and the way the study was powered, the main focus of the statistical analysis will be estimation of the incidences of birth defects and spontaneous abortion. 95% confidence intervals will be computed around these incidences in order to judge whether there is an increase of these incidences as compared to background risks.

In order to control for potential confounders, birth defects and spontaneous abortion will be described according to parameters such as concomitant infections/diseases and medication use. For spontaneous abortions, women who discontinued the study prior to delivery will not be taken into account in the primary analysis. A sensitivity analysis will be performed considering all patients, assuming that women who discontinued the study prior to delivery had experienced spontaneous abortion; this will provide us with the highest estimation of incidence of spontaneous abortion (i.e. the worst-case scenario).

In the same way, in the primary analysis, incidences of birth defects will be analysed without considering patients who discontinued the study prior to 14 weeks after the end of pregnancy. A sensitivity analysis will be performed on all patients assuming that women who discontinued the study prior to 14 weeks after the end of pregnancy had experienced birth defects.

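### The primary incidences pool women whose fetal status or pregnancy outcome was already known at enrolment, which can be expected to raise the birth-defect incidence

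*Protocol*

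**What the plan says.** **Eligibility.** Section 6.1 (Patient's representativeness) warns that "patients with a known undesirable outcome may be more likely to enroll than" those with a known healthy outcome. It then decides, because recruitment may be difficult, that "women who already know the health status of the foetus at the time of enrolment into the pregnancy registry will still be eligible". The criteria in Section 5.2 exclude neither known fetal status nor a completed pregnancy.

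**Enrolment data.** Section 5.5 (At enrolment visit) collects "Health status of the fetus, if it is already known at time of enrolment, i.e. via ultrasound" and also "Pregnancy outcome, if already known at time of enrolment".

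**Other entry routes.** Section 5.3 states that "all patients with pregnancies reported to the company as spontaneous events by HCPs will also be asked to participate". Section 5.3.1 adds: "A review of literature will be performed routinely to ensure that HCPs publishing any relevant maternal exposure are contacted for inclusion". Either route can bring in a pregnancy whose outcome is known.

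**Analysis.** Under Section 5.7, "All analyses, primary and secondary, will be conducted in two manners": on all women, and stratified by whether the woman or the biological father was exposed. In the primary analysis, "the main focus of the statistical analysis will be estimation of the incidences of birth defects and spontaneous abortion", with 95% confidence intervals compared with background risks. The sensitivity analyses specified there deal with discontinuation only. Further breakdowns are by trimester, demographics, medical background, lifestyle, concomitant disease and medication, and first or recurrent malaria. Section 5.4 mentions a sensitivity analysis for other contributing factors without naming them.

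**The concern.** A woman who joins after learning that her fetus or infant is affected was not followed from a point at which the outcome was open. If such women are readier to join, their share of affected pregnancies exceeds that of all exposed pregnancies, and pooling carries the excess into the primary estimate. The comparator is an external background rate, so no internal control group shares the bias and cancels it.

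Section 6.1 gives recruitment as its reason for enrolling these women. That does not justify counting them in the primary incidence. Section 5.7 fixes the analysis sets for all analyses, so a statistical analysis plan that follows the protocol inherits the pooling. At stake is whether an apparent rise in birth defects could come from the way women entered the registry.

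**Working it through.** **Inputs from Section 5.4.** Background birth-defect rate p0 = 23.719/1,000 = 0.023719; 2-fold alternative p1 = 0.047438; one-sided 5% level, 80% power, 5% loss to follow-up, 376 women.

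**Reproducing 376.** With an exact one-sample binomial test, the smallest n reaching 80% power is 357, signalling at 14 or more cases (one-sided level 4.8%, power 80.1%). Then 357/0.95 = 375.8, rounded up to 376. The normal approximation that Section 5.4 names gives 328, or 346 with loss to follow-up. That difference does not affect this point. I use n = 357.

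**Decision rule.** Section 5.7 uses 95% confidence intervals and two-sided hypotheses; the one-sided level belongs to the sizing. The protocol does not name the interval method, so I take the exact one. The lower limit for x cases is the 2.5% quantile of Beta(x, n − x + 1):

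- x = 14: 0.0216
- x = 15: 0.02370, just below 0.023719
- x = 16: 0.0258

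A signal therefore needs 16 or more cases. With no drug effect and no bias, 357 × 0.023719 = 8.5 cases are expected, and P(X ≥ 16) = 1.2%.

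**Effect of pooling (assumed inputs).** Let a share f of women have known status, with k times the background rate. The protocol gives neither f nor k. The case count is the sum of Bin((1 − f)·357, p0) and Bin(f·357, k·p0), and the pooled rate is p0 × [(1 − f) + f·k].

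| f | k | Pooled rate ÷ p0 | P(X ≥ 16), exact 95% CI rule | P(X ≥ 14), one-sided sizing rule |
|---|---|---|---|---|
| 0 | – | 1.00 | 1.2% | 4.8% |
| 10% | 1.5 | 0.90 + 0.15 = 1.05 | 1.9% | 6.6% |
| 10% | 3 | 0.90 + 0.30 = 1.20 | 5% | 14% |
| 10% | 5 | 0.90 + 0.50 = 1.40 | 14% | 30% |
| 20% | 3 | 0.80 + 0.60 = 1.40 | 14% | 30% |
| 20% | 5 | 0.80 + 1.00 = 1.80 | 45% | 66% |
| 30% | 5 | 0.70 + 1.50 = 2.20 | 77% | 90% |

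**A second model.** Suppose affected known-status pregnancies are k times as likely to enrol as healthy ones. Their rate is then k·p0/(k·p0 + 1 − p0). For k = 3 this is 0.0679. With f = 25% the pooled rate is 0.25 × 0.0679 + 0.75 × 0.0237 = 0.0348, or 1.47 times background, and the exact 95% CI rule signals with probability 18%.

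**Cost of separating the groups.** Power under the one-sided sizing test, by normal approximation, is Φ{[√n(p1 − p0) − 1.645√(p0(1 − p0))]/√(p1(1 − p1))}:

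- n = 357: 82%
- n = 321 (10% known-status): 79%
- n = 268 (25%): 74%
- n = 178 (50%): 62%

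**The case against.** Several points on the other side stand.

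- **The bias is disclosed and hedged.** Section 6.1 says that it could occur and that such women may be more likely to enrol. A reader might infer that the incidence is certainly inflated, or by a known amount. The protocol supports an expected direction for birth defects and no size. For spontaneous abortion, Section 6.2 expects some early losses to go unrecognised or unreported, which lowers the incidence.
- **The effect may be small.** At a 10% share and 1.5 times background, the false-signal probability rises only from 1.2% to 1.9%. Quoting only the 14-case rule would overstate the absolute figures, because that is the sizing test and not the rule of Section 5.7.
- **Entry route is not the same as known outcome.** A reader might infer that spontaneous reports and published cases are all outcome-driven, since Section 5.3 mentions birth defects. That example stands in the sentence on what will be reported, beside pregnancy exposure, and not in the sentence on who is invited. A reported or published exposure may be an ongoing pregnancy with unknown outcome.
- **There are safeguards.** Consecutive inclusion and the log of non-included patients (Sections 6.1 and 7.2) help in part. They cover patients whom a participating provider sees, and pregnancy outcome is not among the log items given as examples.
- **The groups can be separated later,** because known status is recorded. This makes the remedy easy, but Section 5.7 does not call for the separation.

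None of these points justifies pooling in the primary estimate.

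**Conclusion.** The concern holds in this form: the protocol names a selection mechanism tied to the outcome, admits the affected women, and pools them into primary incidences that are judged against external rates, with no analysis by knowledge at enrolment. Upward bias is to be expected for birth defects; the net direction for spontaneous abortion is unclear.

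Its size cannot be derived from the protocol. Over the assumed range, the false-signal probability under the exact 95% interval runs from barely changed to 77%. At a 20% share with 5 times the background rate, the pooled rate is 1.8 times background with no drug effect, close to the 2-fold rise the registry is sized to detect. These figures assume 357 evaluable women, independent outcomes and a correct background rate.

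**What to change.** In Section 5.7, define the primary incidence set as pregnancies whose outcome and fetal health status, normal or abnormal, were both unknown at enrolment, whatever the entry route. Report pregnancies with known status or outcome separately, and give the pooled all-women incidence as a sensitivity analysis.

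Two shortcuts should be avoided. Removing only women with an abnormal prenatal finding, while keeping those with a normal one, selects on the outcome and biases the incidence downward. Removing every spontaneous or literature case discards ongoing pregnancies with unknown status.

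Eligibility and data collection stay as they are. The change needs wording in Section 5.7 and one variable derived from the enrolment form. The cost is precision: power for a 2-fold rise in birth defects falls from about 82% to 79% or 74% if 10% or 25% of women have known status, and further if the share is larger. Holding 376 in the primary set would mean enrolling about 376/0.90 = 418 or 376/0.75 = 502 women. Sections 6.1 and Appendix 1 already name recruitment as the main limitation, so Section 5.4 should instead restate the power for the reduced primary set.
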